5.5.3.2. Other endpoints

All other endpoints are binary variables: stillbirths, live births, full term delivery, pre-term and post-term delivery, small for gestational age, large for gestational age, birth defects and baby's death.

The proportion of each outcome will be computed for the exposed and non-exposed cohorts as the number of cases divided by the total number of subjects with known pregnancy outcome. An exact 95% CI will be computed.

The exposed and non-exposed cohorts will be compared using logistic regression with the pregnancy outcome as the dependent variable, a dichotomous exposure as the independent variable and the age at first day of gestation as a covariate. The odds ratio (OR) and its 95% CI will be derived.

Baby characteristics will be summarized per cohort using descriptive statistics: n of non-missing observations, mean, standard deviation, minimum and maximum for continuous variables (birth weight and length) and frequency table (n, %) for categorical variables (sex, Apgar score at 1 and 5 min).

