4.3. Included population

It is planned to include all eligible pregnant women in each of the two cohorts.

All included subjects will be followed until: end of pregnancy, subject de-enrolment from CPRD *GOLD* or study termination.

(Amended 14 March 2013)

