5.4. Sample size calculation

Using a two-sided log-rank test with type I error rate of 5% (Software: PASS 2005) and results from the feasibility analysis which has estimated the potential eligible subjects (see section 3.2), the study would have the following power to detect a relative risk (Hazard ratio, HR) of 2.0 of spontaneous abortion between the exposed and non-exposed subjects: 98% power if the first day of LMP is between 30 days before and 45 days after and 99% power if the first day of LMP is between 30 days before and 90 days after any dose of *Cervarix*. The HR detectable with 80% power would be 1.69 and 1.60, respectively.

Those calculations are based on the following assumptions:

- Rate of spontaneous abortion: approximately 11.5% of pregnancies (see section 3.2, feasibility analysis).
- Proportion of dropped out subjects before the first 23 weeks of gestation: 20%.

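### The known-outcome denominator understates live birth and full term delivery, because women who de-enrol while pregnant are dropped and early-ended pregnancies are kept; section 5.6.2 sets a conflicting denominator

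*Combined protocol and SAP*

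**What the plan says.** Section 5.5.3.2 opens with "All other endpoints are binary variables: stillbirths, live births, full term delivery" and goes on to the remaining outcomes. The proportion for each is "the number of cases divided by the total number of subjects with known pregnancy outcome", with an exact 95% CI. Cohorts are compared by logistic regression on exposure and age at first day of gestation, without follow-up time. Section 5.6.3.2 again lists live birth and full term delivery among the outcomes to be modelled. It does not say which women enter the model or how an unknown outcome is coded. Section 5.6.1 rules out substitution of missing data.

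Women can leave while pregnant. Section 4.3 reads "All included subjects will be followed until: end of pregnancy, subject de-enrolment from CPRD" GOLD, or study termination. Section 5.4 assumes "Proportion of dropped out subjects before the first 23 weeks of gestation: 20" per cent; it gives no split by cohort and no figure after week 23.

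For spontaneous abortion, sections 5.2.5.3 and 5.6.3.1 censor at de-enrolment. Nothing equivalent is planned for the outcomes in 5.5.3.2. Section 5.6.2, covering all pregnancy outcomes, uses the total number of pregnancies as the denominator instead.

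**The concern.** Whether an outcome is known depends on how long the pregnancy lasts. A loss at week 10 is known if the woman stays registered for 10 weeks, while a live birth requires about 40. Most women who de-enrol while pregnant would have gone on to deliver. Removing them from numerator and denominator leaves a set enriched for early endings. This happens even if leaving has nothing to do with the pregnancy, and adjusting for age does not correct it.

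At stake are the live-birth and full-term proportions and their exact intervals, which would be centred on values that are too low. If the cohorts leave the database at different rates, the live-birth odds ratio would also move away from 1 with no vaccine effect, which in a safety study could create or mask a signal.

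**Working it through.** **1. The plan's own figure.** The documents give no planning figure for live birth. The only calculation that uses the drop-out rate is the primary power statement in 5.4: "Using a two-sided log-rank test with type I error rate of 5" per cent, "power to detect a relative risk (Hazard ratio, HR) of 2.0", with "98% power if the first day of LMP is between 30 days before and 45 days after and 99% power" for the wider window. Inputs are 243 or 379 exposed and 667 non-exposed (section 3.2), and 11.5% spontaneous abortion (5.4). Freedman's formula is z = √D × (HR−1)√φ / (1+φ·HR), where φ is exposed/non-exposed and D is the expected number of events.

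- Narrow window, no drop-out: D = 243 × (1−0.885²) + 667 × 0.115 = 129.4, φ = 0.364, z = 3.97, power Φ(3.97−1.96) = 97.8%.
- Wide window, no drop-out: D = 158.9, φ = 0.568, z = 4.45, power 99.4%. Detectable HRs at 80% power are 1.68 and 1.59.
- With 20% competing drop-out: power about 96% and 99%, detectable HRs 1.72 and 1.63.

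The plan states: "The HR detectable with 80% power would be 1.69 and 1.60, respectively". Both versions come within 2 points of the stated power, so the inputs are understood. The check does not show what the 20% consists of.

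**2. Closed form for live birth.** Assumptions: the 20% is non-informative loss at a constant hazard through term; early endings fall at day 70 and live births at day 279.

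- h = −ln(0.8)/161 = 0.001386 per day; S(t) = exp(−ht).
- S(70) = 0.907; S(279) = 0.679.
- The true odds of live birth are multiplied by S(279)/S(70) = 0.749.
- With early loss of 11.5% only (true live birth 88.5%): 0.885 × 0.679 = 0.601 known live births and 0.115 × 0.907 = 0.104 known early endings. Known-outcome proportion = 0.601/0.705 = 85.2%, an understatement of 3.3 points.
- If drop-out stops at day 161, the factor is 0.800/0.907 = 0.882 and the result is 87.2%, an understatement of 1.3 points.

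**3. Fuller model.** Spontaneous abortion is 11.5% on days 35–112, stillbirth 0.5%, and induced abortion 0, 20 or 40% on days 42–98. The stillbirth and induced-abortion rates and all timings are assumptions. Drop-out is 20% by day 161 at a constant hazard.

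| Induced abortion | True live birth | Known-outcome (5.5.3.2) | All pregnancies (5.6.2) | Aalen-Johansen |
|---|---|---|---|---|
| 0% | 0.880 | 0.848 | 0.602 | 0.880 |
| 20% | 0.680 | 0.617 | 0.465 | 0.681 |
| 40% | 0.480 | 0.411 | 0.328 | 0.479 |

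The understatement under 5.5.3.2 is 3 to 7 points. If drop-out stops at week 23 the values are 0.867, 0.653 and 0.449, or 1 to 3 points low. Full term delivery behaves alike: 0.744, 0.541 and 0.361 against true 0.774, 0.598 and 0.422. The 5.6.2 denominator does worse because women who leave count as not having a live birth.

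**4. Odds ratio with no true effect.** The known-outcome OR is the ratio of S(279)/S(70) between cohorts, which equals [(1−d₁)/(1−d₀)]^(209/161), where d is drop-out by day 161 and 209 = 279−70.

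- Equal drop-out: OR 1.00.
- 15% vs 25%: (0.85/0.75)^1.298 = 1.18; reversed, 0.85.
- 18% vs 22%: 1.07.
- 15% vs 25% with drop-out stopping at day 161: exponent 91/161, OR 1.07; reversed, 0.93.

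The fuller model gives 1.17 and about 0.86 for 15% vs 25%. With drop-out as extreme as 30% exposed vs 10% non-exposed, it gives 0.73–0.74 for live birth, 0.74–0.82 for full term, 0.88–1.02 for pre-term and 0.90–1.04 for stillbirth.

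**The case against.** The strongest reply is that the known-outcome rule is neither the only denominator in the plan nor clearly the one used in the models. Section 5.6.2 uses all pregnancies, 5.6.3.2 is silent, and the known-outcome set for the logistic model is inferred from 5.5.3.2 together with the no-substitution rule. That stands. It does not rescue the plan, since the 5.6.2 version has the larger bias and the two sections must be reconciled in any case.

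Second, live birth and full term delivery are not among the secondary endpoints listed in 5.1.2; they appear only as analysed outcomes. This also stands and limits the weight of the point, but 5.5.3.2 and 5.6.3.2 do commit to estimating and comparing them.

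Third, the level bias depends on how the 20% is read. It is a planning value up to week 23 for a log-rank calculation, and may include censoring at induced abortion. Extending it to term is an assumption. The range of sizes above reflects this.

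Fourth, a reader might infer that the planned odds ratios are biased. The documents do not support that. They give one overall drop-out rate, both cohorts share the same LMP window, age limits and 12-month registration rule (4.2.2.1, 4.2.2.2), and the expected age difference is about one year (3.2). With about 180 and 494 known outcomes and 69% live birth, the SE of the log OR is about 0.19, so an OR of 1.18 is about 0.9 SE from the null and 1.07 about 0.4 SE. The odds-ratio concern is conditional on a drop-out difference that only the data can show.

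**Conclusion.** The point holds for live birth and full term delivery expressed per pregnancy. As planned, the proportion and its exact 95% CI are biased downward even when drop-out is non-informative. A true 88.5% live birth becomes about 85% if the 20% is loss to follow-up at a constant hazard through term. The understatement is about 3 to 7 points across assumed rates of other early endings that the documents do not give, about 1 to 3 points if drop-out stops at week 23, and less if the 20% includes induced abortions. The null OR remains 1.00 under equal drop-out; it moves to about 1.18 or 0.85 under an assumed 15% vs 25%, and nearer 1 if drop-out stops at week 23.

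A reader might extend this to every outcome in 5.5.3.2 or to the primary result. Neither follows. Stillbirth and pre-term delivery move little and in either direction, and the spontaneous-abortion Cox model already censors at de-enrolment. The plan should be changed, but this is not a threat to the study's main conclusion.

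**What to change.** 1. Reconcile 5.5.3.2 and 5.6.2 so that one denominator is defined for each outcome.
2. For live birth and full term delivery, report the Aalen-Johansen cumulative incidence by cohort, treating the other pregnancy endings as competing events and censoring at de-enrolment, with its 95% CI in place of the exact binomial interval.
3. In 5.6.3.2, fit the age-adjusted logistic model for these two outcomes with each known-outcome pregnancy weighted by the inverse of the cohort-specific Kaplan-Meier probability of still being registered on the outcome date. Use a variance that allows for the weights.
4. State the logistic analysis set and how unknown outcomes are treated. Tabulate unknown outcomes by cohort, separating women who de-enrolled from women still registered with no recorded outcome; the weights address only the former.

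The correction relies on de-enrolment being non-informative within cohort. The cost is some SAP wording, a little programming and slightly wider intervals. No new data are needed: registration information is already extracted (5.2.4.1) and the de-enrolment date is already required for the Cox censoring. Limiting the denominator to women registered to day 301 would be simpler, but is not advised: at the assumed hazard S(301) = 0.659, so it would discard about a third of the women.

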5.6. Statistical calculations

All the statistical calculations will be done in SAS 9.2 or higher.

All the statistical tests will be two-sided at alpha level of 0.05.

5.6.1. Handling of missing data

Missing data will not be substituted.

5.6.2. Descriptive statistics

Age at first day of gestation will be summarized by descriptive statistics per cohort (exposed and non-exposed) and overall: n of subjects, mean, standard deviation (SD), median, minimum and maximum and compared between the two cohorts using a student t-test.

Smoking status (smoker vs. non-smoker), alcohol consumption (Yes/No) will be summarized in frequency tables (n, %) per cohort and overall. The two cohorts will be compared using a Fisher's exact test.

Diabetes and high blood pressure will be summarized in frequency tables (n, %) per cohort and overall. The two cohorts will be compared using a Fisher's exact test.

First day of LMP occurring during the H1N1 pandemic (01JUN2009 to 28FEB2010) will be summarized in frequency tables (n, %) per cohort and overall. The two cohorts will be compared using a Fisher's exact test.

Exposure to other vaccines will also be summarized in frequency tables per cohort and period (within 3 months before first day of gestation and during the 1st trimester of gestation).

Number of subjects exposed to contra-indicated drugs during the 1st trimester of gestation will be tabulated per cohort and overall.

All the pregnancy outcomes (see section 5.2.4.2) and birth defects (see section 5.2.4.3) will be summarized by descriptive statistics per cohort. The statistics will be computed:

- Number of cases
- Proportion computed as the number of cases divided by the total number of pregnancies

All the cases of pregnancy outcome including outcomes with apparent birth defects and baby's deaths will be listed with data about exposure status, age at first day of gestation, gestational age at the event date, smoking status, alcohol consumption, diabetes, high blood pressure, exposure to other vaccines, to contra-indicated drugs and H1N1 pandemic.

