3.2. Feasibility analysis and limitations of the study design

A feasibility analysis of HPV vaccination records and pregnancy outcomes data in CPRD *GOLD* database was performed by GSK.

Immunization with HPV vaccine is coded in the CPRD *GOLD* with the following codes: 93489, 93621, and 95554 for the 1st, 2nd and 3rd dose, respectively.

Exploration of the CPRD *GOLD* database identified 148,731 vaccinated subjects (Table 2) and 83,686 aged between 15 and 25 years (Table 3).

Table 2 Counts of HPV vaccination per year in the CPRD *GOLD*

Year of vaccination	N
2007	247
2008	29,301
2009	87,233
2010	29,364
2011	2,586

Created by GSK Biologicals, 2012

Data extracted from CPRD *GOLD* version ffcprd_smart_2012Q3

Table 3 Number of HPV vaccinations per age range in the CPRD *GOLD*, 2007-2011

Age Range	N subjects HPV
9-14	64,667
15-19	82,382
20-25	1,304

Created by GSK Biologicals, 2012

Data extracted from CPRD *GOLD* version ffcprd_smart_2012Q3

However, data on HPV vaccination status is not captured for all vaccinees in CPRD *GOLD* (lack of sensitivity) and absence of a vaccination record does not imply absence of vaccination. For instance, 70.7% of the 01SEP1996 – 31AUG1997 birth cohort was reported as HPV vaccinated in CPRD *GOLD* vs. 85.9% reported by the UK Health Protection Agency (HPA). Corresponding numbers for the 01SEP1994 – 31AUG1995 birth cohort are 70.6% vs. 81.9% (Table 4).

Table 4 HPV vaccination coverage in CPRD GOLD and HPA data

Birth Cohort	CPRD GOLD **			UK*
	N vaccinated	N total	%	%
01SEP1996 and 31AUG1997	16,028	22,685	70.7%	85.9%
01SEP1994 and 31AUG1995	16,343	23,143	70.6%	81.9%

Created by GSK Biologicals, 2012

*From Health Protection Agency Department of Health [Health Protection Agency, 2012]

** Data extracted from CPRD **GOLD** version ffcprd_smart_2012Q3

To overcome this limitation related to incomplete vaccination records, the non-exposed cohort will include *Cervarix* vaccinated women who have had the first day of gestation between 120 days and approximately 18 months after the last *Cervarix* dose. That would increase the specificity in the control group since it would be very unlikely for women to be vaccinated again after completing the three HPV doses. This is also the design agreed with the FDA for the study in the US (EPI-HPV-020).

Contrary to the lack of sensitivity in the overall population, a lack of specificity in the vaccine records is very unlikely, because vaccination is an important event.

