4. STUDY POPULATION

4.1. Study cohorts

Two cohorts of pregnant women will be defined based on exposure to *Cervarix* as recorded in the CPRD **GOLD** (Figure 1) **(Amended 14 March 2013)**:

- The **exposed cohort** will include women with the first day of LMP: between 30 days before and 45 days after any *Cervarix* dose, as requested by the FDA, and between 30 days before and 90 days after any *Cervarix* dose, as defined in the study EPI-HPV-020 and as used for the pooled analysis by Wacholder [Wacholder, 2010].
- The **non-exposed cohort** will include women with the first day of LMP between 120 days and 18 months after their last *Cervarix* dose (and no further *Cervarix* dose before the outcome).

Figure 1 Definition of exposure and non-exposure

Note: Last dose can be first or second dose if no subsequent dose was administered.

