5.5.2. Demographic and baseline characteristics

Demographic and baseline characteristics of all included subjects (age at first day of gestation, age at vaccination, marital status, smoking, alcohol consumption, region (GP practice)) will be summarized per cohort and overall, using descriptive statistics.

Frequency tables will be generated for categorical variables.

Mean, standard error, median and range, will be provided for continuous variables.

Medical condition during pregnancy (diabetes, high blood pressure) will be summarized in a frequency table.

Availability of data in CPRD **GOLD** will be summarized by descriptive statistics: proportion of Baby and Mother links.

Proportion of subjects with first day of LMP before, during and after H1N1 pandemic in the UK (June 1st 2009 to February 28th 2010 according to Pebody [Pebody, 2010]).

The two cohorts will be compared for their demographic and baseline characteristics using Fisher's exact test or Student t-test.

(Amended 14 March 2013)

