5.6.3. Statistical models

5.6.3.1. Cox proportional hazards model

Cox model will be computed using the SAS PHREG procedure. The dependent variable is the time between first day of gestation and the event or at censoring.

For the spontaneous abortion analysis, time to event for subject with no spontaneous abortion will be censored at the earliest of the following time-points:

- 161 days (end of week 23) or 133 days (end of week 19)
- Lost-to-follow up (*de*-enrolment from CPRD *GOLD*) (**Amended 14 March 2013**)
- Mother's death
- Pregnancy termination

The main model (Model 1) will include the exposure status (exposed vs. non-exposed) as a binary independent variable and the age at first day of gestation as a continuous covariate. The adjusted HR will be derived as the exponential of the coefficient associated with the exposure status and its 95% Wald CI.

Survival curve will be depicted for the exposed and non-exposed cohort (using the Option Plots(overlay)=survival in the SAS PHREG procedure).

The following models will also be computed as sensitivity analyses:

Model 2: A Cox model including, in addition to the age at first day of gestation, other covariates

- Smoking during pregnancy (3 classes: yes, no, unknown)
- Exposure to H1N1 pandemic (yes, no)
- Region (class variable)
- Alcohol consumption during pregnancy (3 classes: yes, no, unknown)
- Diabetes during pregnancy (3 classes: yes, no, unknown)

- High blood pressure during pregnancy (3 classes: yes, no, unknown)
- Number of previous pregnancies (sum of the number of previous births and the number of previous abortions)
- Vaccination with another vaccine within 90 days before first day of gestation or within the 90 days after first day of gestation (binary variable)
- Use of contra-indicated drugs during the first trimester of pregnancy (three classes: non contraindicated drug, manufacturer advice “to-use with caution” drugs, manufacturer mentioned advice “to-avoid” drugs)

Covariates occurring in less than 5% of the subjects (percentage will be computed over both exposed and non-exposed cohorts) will not be included in the model.

Model 3: A Cox model will compare the exposed cohort according to the number of *Cervarix* doses (3 classes: 1 dose, 2 doses, 3 doses) vs. the non-exposed cohort, using the same model as for the primary analysis (model 1). In this model, the exposed women with more than 3 doses of *Cervarix* will not be included.

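### H1N1 exposure is coded from the LMP date alone, so Model 2 misses pandemic time in pregnancies that began before June 2009, which fall mostly in the exposed cohort (minor; primary HR unaffected)

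*Combined protocol and SAP*

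**What the plan says.** The pandemic variable appears in four places in the combined protocol and SAP.

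- Section 5.5.2 plans a three-class baseline summary: "Proportion of subjects with first day of LMP before, during and after H1N1 pandemic in the UK (June 1st 2009 to February 28th 2010").
- Section 5.6.2 plans a two-class comparison by Fisher's exact test: "First day of LMP occurring during the H1N1 pandemic (01JUN2009 to 28FEB2010) will be summarized in frequency tables".
- Section 5.5.3.1 lists the pandemic among the extra covariates of the sensitivity Cox regression.
- Section 5.6.3.1 (Model 2) enters it as "Exposure to H1N1 pandemic (yes, no"), a fixed two-class covariate.

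Only 5.5.2 and 5.6.2 say how the variable is derived, and both use the LMP date. No time-dependent or overlap rule is given. Appendix A, which holds the derivation algorithms, is named, but its contents are not in the available text.

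Follow-up for the Cox models is censored at "161 days (end of week 23) or 133 days (end of week 19"). In section 4.1, the primary exposed window puts the LMP "between 30 days before and 45 days after any" dose, and non-exposed women have the "first day of LMP between 120 days and 18 months after their last" dose.

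**The concern.** The covariate is meant to capture a pregnancy being at risk while the pandemic was under way. The LMP date marks only the first of up to 161 at-risk days. A woman with LMP in April 2009 passes most of her risk period inside the pandemic and is coded 'no'. A woman with LMP in late February 2010 has almost none of hers inside and is coded 'yes'.

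The error would matter less if it fell equally on the two cohorts. It does not. Exposed LMPs sit around dose dates from September 2008 onward, whereas non-exposed LMPs begin at least 120 days after the last dose. Pregnancies that began shortly before June 2009 are therefore concentrated in the exposed cohort.

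Model 2 is the only planned adjustment for the pandemic and has no other calendar-time term. A reader could take it as having dealt with pandemic confounding when part of that confounding remains in the exposure HR.

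**Working it through.** The plan gives no figure for this misclassification, so there is none to reproduce.

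**Step 1. Dates (no assumptions).** Section 5.2.4.2 counts the first day of gestation as day 1, so day 161 is that day + 160 and day 133 is that day + 132.

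- First LMP reaching the pandemic: 01JUN2009 − 160 days = 23DEC2008 (23-week endpoint); 01JUN2009 − 132 days = 20JAN2009 (19-week endpoint).
- The missed interval therefore runs from 23DEC2008 (or 20JAN2009) to 31MAY2009.
- Earliest possible non-exposed LMP: first allowed dose 01SEP2008 + 120 days = 30DEC2008.
- For a three-dose completer with about 180 days from first to third dose: 01SEP2008 + 180 = 28FEB2009, and + 120 = 28JUN2009. This is after the missed interval has closed.

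**Step 2. Size by cohort (simulation).** Inputs from the documents:

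- Yearly vaccination counts (section 3.2, Table 2): 29,301 (2008), 87,233 (2009), 29,364 (2010), 2,586 (2011).
- Dose mix from catch-up coverage of 62.2 / 54.2 / 31.8% (section 3.1). One dose: (62.2 − 54.2)/62.2 = 13%. Two doses: (54.2 − 31.8)/62.2 = 36%. Three doses: 31.8/62.2 = 51%.
- Cohort windows (section 4.1) and the eligibility dates 01SEP2008 to 30JUN2011.

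Assumptions: Table 2 dates are first doses, spread evenly within each year (from September in 2008, to June in 2011); doses at 0, 30 and 180 days; LMP uniform over the study period.

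Plausibility check: the modelled ratio of non-exposed to exposed is about 2.5, against 667/243 = 2.74 in section 3.2.

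Results for the −30/+45 window and 161 days:

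| | Exposed | Non-exposed |
|---|---|---|
| LMP before / during / after pandemic | 33 / 41 / 25% | 2 / 24 / 75% |
| Days 1-161 overlap the pandemic | 64% | 25% |
| Overlap, but coded 'no' | 23% (about 55 of 243) | 2% (about 13 of 667) |

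The gap between cohorts is about 18 percentage points by LMP coding and about 39 by overlap.

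Varying the assumptions changes the miscoded share as follows:

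- All 2009 doses in July-December: 8% v 2%.
- All 2009 doses in January-June: 38% v 2%.
- Everyone three doses: 21% v 0%. Everyone one dose: 26% v 5%.
- −30/+90 window: 21.5% v 2.0%. 19-week endpoint: 19.5% v 2.0%.
- The direction reverses (3.2% v 4.7%) only if every woman had one dose and all 2009 doses fell in July-December. That case contradicts the coverage in section 3.1 and gives a cohort ratio of 5.1 rather than 2.74.

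**Step 3. Effect on the Model 2 HR.** Further assumptions: overall loss risk 11.5% (section 5.4), median loss at day 63, no vaccine effect, and a pandemic hazard ratio of 1.3 or 1.5. Week-stratified Poisson models were fitted to the expected events:

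| Pandemic HR | No covariate | LMP coding | Fixed overlap | Time-dependent |
|---|---|---|---|---|
| 1.3 | 1.08 | 1.05 | 1.01 | 1.00 |
| 1.5 | 1.13 | 1.07 | 1.01 | 1.00 |

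On the log scale, LMP coding removes about 41% of the bias. With the same dose mix, the residual HR runs from 1.02 (2009 doses all July-December) to 1.07 (all January-June) at a pandemic HR of 1.3, and from 1.03 to 1.11 at 1.5.

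**Step 4. Against precision.** Expected events are 243 × 0.115 = 27.9 and 667 × 0.115 = 76.7. SE(log HR) ≈ √(1/27.9 + 1/76.7) = 0.22. The base-case bias at a pandemic HR of 1.5 is ln(1.07)/0.22 ≈ 0.3 SE; the largest above is ln(1.11)/0.22 ≈ 0.5 SE.

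**The case against.** Five points on the other side have weight.

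- **The primary analysis is untouched.** Model 1 contains only exposure status and age. The covariate enters one sensitivity model. This stands and limits the severity.
- **The pandemic effect is assumed.** The documents give no effect of H1N1 on spontaneous abortion. If there is none, there is no bias. This stands; the HRs above are illustrations.
- **The bias is small.** It is at most about half a standard error in the cases run with the documented dose mix, and section 5.4 puts the HR detectable with 80% power at 1.69. This also stands.
- **Appendix A might define the Model 2 covariate differently.** That is possible and should be checked. Both definitions in the available text use the LMP date, so this is the natural reading.
- **The calendar imbalance would be visible anyway.** A reader might infer that the baseline tables would make the cohorts look balanced on the pandemic. The documents do not support that. The before/during/after summary in 5.5.2 would show the difference plainly (about 33% v 2% before the pandemic in the base case), and even the two-class comparison shows 41% v 24%. What remains true is that the two-class comparison understates the imbalance in at-risk time.

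A reader might also infer that LMP coding removes only about a fifth of the confounding. That figure belongs to the case where everyone has one dose and doses are spread evenly within each year. With the documented dose mix it is about 41%, and it ranges from roughly 2% to 77% with the timing of the 2009 doses, which the documents do not report.

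None of these points offers a reading in which the LMP date captures pandemic exposure over days 1-161.

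**Conclusion.** The point holds as a minor one. The only definition in the available text misses pandemic exposure for LMPs from 23DEC2008 to 31MAY2009, and the cohort windows concentrate that error in the exposed cohort. The dates follow from the plan itself. The 23% v 2% rests on assumed dose timing and spacing; with the documented dose mix, the miscoded share is about four times or more higher in the exposed cohort in every timing tried. The residual HR of about 1.05 or 1.07 also rests on an assumed pandemic effect, and it points towards apparent vaccine harm.

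It would be wrong to conclude that the primary result is biased by this coding, or that Model 2 could create or hide an effect of the size the study was designed to detect. The weakness is that Model 2 adjusts only partly for a factor the plan chose to adjust for.

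**What to change.** In Model 2, replace the LMP-date variable with a time-dependent indicator equal to 1 on gestational days that fall between 01JUN2009 and 28FEB2010, and 0 otherwise.

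If a fixed covariate is preferred, code 'yes' when days 1-161 overlap that period, i.e. first day of gestation from 23DEC2008 to 28FEB2010 (from 20JAN2009 for the 133-day endpoint). Base the overlap on the planned 161 or 133 days, not on observed follow-up, so that the covariate does not depend on how long the pregnancy lasted. In the base case the fixed version leaves an HR of about 1.01.

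Add the overlap version to the baseline table beside the before/during/after summary, and state the definition in 5.6.3.1 and Appendix A so that they agree.

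The cost is one derived variable and a few lines in PHREG. All the dates are already extracted, and no other analysis changes.
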